Secondary endpoints	
CAAD for five sub-categories of CID (RTI, UTI, skin, GI unexplained fever); number, site, duration (mean and cumulative) of infection; incidence and duration of diarrhoea;
 
EQ-5D (health utility), ICECAP-O (wellbeing); hospitalisations; death;
 
Antimicrobial resistance (AMR) (Culture and antibiotic sensitivity of Gram-negative Enterobacteriaceae and VRE from stool sample and presence of probiotic species in stool to explore adherence and contamination); Antibiotic consumption
 
Mechanistic measures:
 
Blood – FBC and immune cell phenotypes; influenza vaccine response - Haemagglutination inhibition assay; immunology - plasma cytokines and chemokines, TLR2 and TLR4 ligand stimulated cytokines/chemokines, monocyte and neutrophil phagocytosis of E. coli; Vitamin D
 
Saliva – presence of oral Candida species
 
Stool – presence of probiotic bacteria Lactobacillus rhamnosus, LGG and Bifidobacterium animalis subsp. lactis, BB-12, plus presence of AMR bacteria and C. difficile
 
Tertiary outcome: To determine if level of serum vitamin D correlate with colonisation of AMR bacteria in faecal isolates (see section 5).
 
Qualitative sub-study to understand how the trial was conducted within the care home context and identify the mechanisms which affect implementation of trial activities.

Interventions	Daily dose for 12 months of study product - probiotic or matching placebo, or until 31/10/18, whichever is sooner.

[figure not shown]

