Hospitalisation	NHS service use	In relation to infections; number of hospital stays for all-cause hospitalisation (as recorded in care home records and discharge summaries)	In a 12 month* period (data recorded at regular intervals by RN from care home records)
Mortality	Mortality rates	Total number of deaths of trial participants (collected from care home records)	In a 12* month period (data recorded at regular intervals by RN from care home records)
Antimicrobial resistance	Gastrointestinal colonisation with antimicrobial resistant (AMR) bacteria	Culture and antibiotic sensitivity of Gram-negative Enterobacteriaceae and vancomycin resistant enterococci (VRE) from stool sample	Samples taken at baseline, 3* and 12* months
Oral microbiology	Levels of oral Candida	Semi quantitative analysis of oral rinse or saliva samples	Samples taken at baseline, 3* and up to 12* months
Influenza vaccine response (for those who have received influenza vaccine only)	Influenza vaccine efficacy	Blood sample - Haemagglutinin inhibition assay and antibody titers	Sample taken on the day of (or up to 10 days prior to), and 4 weeks (28 days) post influenza vaccination (trial participants need to have been on Study Product for at least 2 months prior to influenza vaccination to take part in this sub-study)
Immunology (ex-vivo responses to	Participant's cytokine and chemokine response in whole	Response measured by laboratory analysis in whole blood (stimulated ex-vivo by TLR2 and TLR4 agonists)	Baseline and up to 12* months

pathogenic challenge) (n≈100)	blood samples stimulated ex-vivo by TLR2 and TLR4 agonists  Participant's plasma cytokines and chemokines  Participant's monocyte and neutrophil phagocytosis of E.coli	Measurement of plasma cytokines and chemokines in plasma and whole blood  Measurement of monocyte and neutrophil phagocytosis of E.coli	Baseline and up to 12* months  Baseline and up to 12 months*
Gut microbiology	Quantify the amount of probiotic in stool samples	Investigative work to analyse level of Lactobacillus rhamnosus , LGG and Bifidobacterium animalis subsp. lactis , BB-12 from stool sample	Samples taken at baseline, 3* and up to 12* months
Haematology and Biochemistry	Haematology; biochemistry	Full blood count (FBC) including immune phenotyping; vitamin D	FBC and Vitamin D at Baseline (all participants); FBC on n≈100 (immunology participants only) and up to 12 months

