### **12.1 Adherence**

Data regarding participant's adherence to the study product will be collected from a number of sources:

- MAR sheets - administration of the study product will be recorded by care home staff using Medication Administration Record sheets (MAR sheets) and monitored by RNs during their visits to each care home. MAR sheet are used in most care homes and will allow incorporation of trial procedures into routine practice easily. If MAR sheets or an equivalent recording system is not used routinely by any care home participating in the PRINCESS trial the research team will provide MAR sheets and training as appropriate.
- Presence of probiotic organisms in bowel - the presence of the probiotic organisms will be assessed in stool samples of participants at baseline, three and up to 12 months. This will give an indication of adherence, survival of the probiotic in the large bowel and potential contamination in the placebo arm.
- Capsule count - regular counts of unused study product will be undertaken by the PRINCESS trial research nurses.

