Clostridium difficile in stools	Two logistic regressions (stool sample finding at 3/12 months separately) controlling for baseline stool sample finding.	
Presence of oral candidiasis	Two logistic regressions (response at 3/12 months separately) controlling for baseline response.	
Amount of oral candidiasis present in saliva	Two ordinal regressions (response at 3/12 months separately) controlling for baseline response.	
L. rhamnosus GG in stools	Two linear regressions (stool sample finding at 3/12 months separately) controlling for baseline stool sample finding.	Transformations for normality.
Bifidobacterium animalis subsp. lactis (BB-12)	Two linear regressions (stool sample finding at 3/12 months separately) controlling for baseline stool sample finding.	Transformations for normality.
Full blood count	Linear regression	Transformations for normality.
Flu vaccine response - titer	Linear regression	Transformations for normality.
Flu vaccine response - seroconversion and seroprotection	Logistic regression	

\* All sensitivity analyses will include a consideration of adherence to study product and the impact of missing data / deaths.

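### Stool LGG and BB-12 are described as presence markers of uptake and placebo-arm contamination, but section 18.2 analyses only their amount

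*Protocol*

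**What the plan says.** The protocol describes this outcome in four places.

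- **Synopsis (section 2), secondary endpoints.** The antimicrobial resistance entry includes "presence of probiotic species in stool to explore adherence and contamination". The mechanistic stool entry lists "presence of probiotic bacteria" and names LGG and BB-12.
- **Section 12.1, Adherence.** Stool is one of three adherence sources, with MAR sheets and capsule counts: "the presence of the probiotic organisms will be assessed in stool samples of participants at baseline, three and up to 12 months". The stated use follows: "This will give an indication of adherence, survival of the probiotic in the large bowel and potential contamination in the placebo arm".
- **Section 5.1, Gut microbiology.** The objective is quantitative: "Quantify the amount of probiotic in stool samples". The outcome measure is the level of each strain.
- **Section 18.2.** The LGG row and the BB-12 row each have one main analysis, "Two linear regressions (stool sample finding at 3/12 months separately) controlling for baseline stool sample finding". The only method-specific sensitivity analysis is "Transformations for normality". Neither strain has a presence row.

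The same table uses logistic regression for Gram-negative isolates, vancomycin resistant enterococci and *C. difficile* in stool. It splits oral Candida in two: "Presence of oral candidiasis" by logistic regression, and the amount in saliva by ordinal regression.

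**The concern.** The protocol puts a yes/no question to this assay: is the strain there in residents given probiotic, and is it absent in those given placebo? The method fixed for it returns one average difference in quantity, which mixes how many residents carry the strain with how much the carriers have.

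This matters most if CAAD shows no difference. The trial will then need to tell apart a product that was not taken or did not survive in the gut, a placebo arm exposed to the same strains, and a product that was taken and retained but had no effect. MAR sheets and capsule counts help with whether the product was taken. They record study product only, so they cannot show gut survival or exposure from elsewhere. Such exposure is plausible on the protocol's own account: section 4.1 notes that some older people already use probiotics, and section 8.3 excludes regular users only if they will not adapt to the trial protocol. Stool presence is therefore the only one of the three listed sources that can speak to contamination.

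**Working it through.** The protocol gives no detection rate, assay limit or power figure for these strains, so there is no stated figure to reproduce. The check compares the sections and then asks what the planned coefficient can contain.

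**1. Purpose against method**

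| Outcome | Presence purpose | Amount purpose | Presence analysis in 18.2 | Amount analysis in 18.2 |
|---|---|---|---|---|
| Oral Candida | Synopsis | 5.1 | Logistic | Ordinal |
| LGG, BB-12 | Synopsis (twice), 12.1 | 5.1 | None | Linear |

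Oral Candida has the same dual purpose and receives both analyses. LGG and BB-12 receive one.

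**2. What the between-arm difference contains**

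Let pA and pP be the proportions detected in the probiotic and placebo arms, m the mean among detected samples (taken as equal in both arms), and c the value given to a non-detect. Then

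difference = (pA − pP) × (m − c).

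Only pA − pP enters. Assume m = 6 on the log10 scale and a detection limit of 10^4:

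| Detected, probiotic v placebo | c = 0 | c = 2 | c = log10(5,000) = 3.70 | c = 4 |
|---|---|---|---|---|
| 40% v 10% | 0.30 × 6 = 1.8 | 0.30 × 4 = 1.2 | 0.30 × 2.30 = 0.69 | 0.30 × 2 = 0.6 |
| 60% v 30% | 1.8 | 1.2 | 0.69 | 0.6 |

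The rows are identical, although the placebo arm has 10% carriers in one and 30% in the other. The same holds untransformed: with every detected sample at 10^6 and non-detects at zero, both cases give 0.30 × 10^6 = 300,000. So this does not depend on the scale or on the non-detect rule.

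The baseline-adjusted linear regression was also simulated, with about 90 per arm (258 × 0.7 / 2 = 90.3, using the 30% drop-out in section 17.2), SD 1 among detects, 10% detected at baseline, and 400 runs per case. Mean estimates agreed with the formula to within 0.02.

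**3. What a presence analysis gives**

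The arm percentages separate the two cases directly: 40% and 10%, against 60% and 30%. The odds ratios are (0.4/0.6)/(0.1/0.9) = 6.0 and (0.6/0.4)/(0.3/0.7) = 3.5. None of these needs a value for a non-detect.

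**4. How far the amount estimate depends on the non-detect value**

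Assume detection of 70% v 5%, detected samples at 10^6 per gram and a limit of 10^3.

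- Untransformed: 0.65 × (10^6 − c) is 649,999 for c = 1, 649,675 for c = 500 and 649,350 for c = 1,000. The spread is about 0.1%.
- Log10: 0.65 × (6 − 0) = 3.90, 0.65 × (6 − 2.699) = 2.15 and 0.65 × (6 − 3) = 1.95. The range is two-fold, but half the limit against the limit differs by only about 10% (2.15/1.95 = 1.10).
- Log10 at 60% v 10% with the limit of 10^4 from step 2: 0.50 × (6 − c) runs from 3.0 (c = 0) to 1.0 (c = 4), a three-fold range.

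The test itself moved little. Across all simulated cases, rejection at the 5% level stayed between 0.92 and 1.00.

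**The case against.** The strongest reply is that section 9 refers the reader to section 5 for the outcome measures, and section 5.1 asks for amount. A linear model of amount fits that objective. This stands, so the point is not that a quantitative model is out of place.

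A reader might go further and infer that the planned main analysis is unstable because it depends on the value given to non-detects. The documents do not support that. The main analysis is not stated to be on a log scale; transformation appears only as a sensitivity analysis, with no form named. Untransformed, the choice hardly matters in the illustration above. On a log scale the dependence is real, but its size rests on detection rates and a limit that the protocol does not give, and the widest ranges need non-detects set far below the limit. A rule for non-detects may also properly sit in the statistical analysis plan.

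A reader might likewise infer that the trial cannot tell whether residents took the product. It can in part: MAR sheets and capsule counts record this, and section 18.1 plans adherence-adjusted structural mean models.

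Finally, an odds ratio alone shares some of the ambiguity: 60% v 10% gives 13.5, and 82% v 25% gives (0.82/0.18)/(0.25/0.75) = 13.7. This also stands, and it is why the percentages by arm are needed beside the model. Nothing in the protocol forbids reporting them, but section 18.2 fixes a method for these two rows and that method leaves presence out.

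**Conclusion.** The point holds as a mismatch inside the protocol. Presence of LGG and BB-12 is a stated endpoint with a stated use, and the analysis table covers only the other stated purpose, amount. A between-arm mean difference cannot show what share of either arm carries the strains. In the illustration, a threefold difference in placebo-arm detection (10% v 30%) leaves the coefficient unchanged. That result assumes equal mean counts among carriers in both arms; the rates themselves are chosen only for illustration.

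The consequence is limited. The outcome is secondary and mechanistic, the primary CAAD analysis is unaffected, and the test for a difference in amount was fairly robust in the cases simulated. What would be lost is a direct answer on uptake and contamination, which the protocol says it wants and which would help to interpret a null result. The change is worth making because it answers a stated question with data already being collected.

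**What to change.** In section 18.2, for each strain:

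- **Add a presence row.** Detected or not detected at the assay limit, at 3 months and at the second follow-up, by logistic regression controlling for the baseline finding, or by an exact comparison if cells are sparse. This follows the pattern of the oral Candida rows.
- **Report the detected percentage in each arm separately at each time point**, with the placebo arm read as contamination and the probiotic arm as uptake.
- **Keep the amount row** for the section 5.1 objective. If amount is log-transformed, treat non-detects as censored at the assay limit (for example with a Tobit model) instead of substituting a value.

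Align the wording of the synopsis, section 5.1 and section 12.1 so that presence and amount are both named. The cost is two added table rows and a few words, with no new samples or assays.

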### **15.3 Trial samples**

**All trial participants:** All trial participants will be asked to provide blood samples at baseline - a full blood count and vitamin D levels will be measured for each participant - the volume of blood taken will be no more than 10ml. At 12 months a full blood count will be measured for around 150 participants - the volume of blood taken will be no more than 4ml.

**Immunology:** For a sample of around 100 trial participants some additional immunology work (detailed in section 5.1) will be done and an additional blood sample will be taken at baseline and up to 12 months – the volume of blood taken will be no more than 6ml at each timepoint. The sample will be taken at the same time as the other blood samples.

**Flu vaccine response sub-study:** A sub-set of patients will be asked to provide a blood sample on the day of (or up to 10 days prior to this), and four weeks (28 days) after they receive their routine seasonal influenza vaccination. For those agreeing to take part in this flu vaccine response sub-study, 5ml of blood will be taken on the day of, and four weeks after receipt of the influenza vaccination, giving a total of no more than 10ml of blood collected.

Blood samples will be taken by the RN who, if needed, will have undergone geriatric phlebotomy training, or by a care home staff member if for example, they are already taking a blood sample for routine care, and/or the care home resident prefers this. The total volume of blood collected during the 6 to 12 month duration of the trial on any one participant will be no more than 36ml.

Each participant will be asked to provide a stool sample at baseline, three months and up to 12 months. The participants normal care provider will be asked to collect the stool samples.

Each participant will be asked to provide a saliva samples (saliva sample or oral rinse) at baseline, three months and up to 12 months.

If participants prefer not to provide any or all of the trial samples listed above this will not be a barrier to their entry to the PRINCESS trial.

All samples will be labelled with the participant unique trial identification number before being sent for analysis. Only fully trained and authorised members of the research team and laboratory staff will have access to the samples. The CI will ensure that the storage, analysis and disposal of all clinical samples will meet the requirements of the Human Tissue Act, 2004.

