## 18.2 Description of outcomes and method of statistical analysis

Outcome	Main analysis	Sensitivity analyses*
Primary		
Cumulative antibiotic administration days (CAAD)	Poisson regression.	Negative binomial regression (if Poisson over-dispersed).
Secondary		
CAAD by infection (UTI, RTI, skin, GI, unexplained fever)	Poisson regression, with trial arm interacted with infection.	Negative binomial regression (if Poisson over-dispersed).
Incidence of infection	Poisson regression.	Negative binomial regression (if Poisson over-dispersed).
Site of infection	Poisson regression, with trial arm interacted with infection.	Negative binomial regression (if Poisson over-dispersed).
Mean duration of infection	A two-level Cox PH (frailty) model with infections nested within participants.	
Cumulative number of infection days	Poisson regression.	Negative binomial regression (if Poisson over-dispersed).
Antibiotic-associated diarrhoea Incidence and duration	Poisson regression.	Negative binomial regression (if Poisson over-dispersed).
All- cause diarrhoea (incidence and cumulative days)	Poisson regression.	Negative binomial regression (if Poisson over-dispersed)
Mean duration of diarrhoea episodes	A two-level Cox PH (frailty) model with infections nested within participants.	
Secondary – Health Utility		
Health utility (EQ5D)	Two linear regressions (EQ5D at 3/12 months separately) controlling for baseline EQ5D.	Transformations for normality.
Well-being (ICECAP-O)	Two linear regressions (ICECAP-O at 3/12 months separately) controlling for baseline ICECAP-O.	Transformations for normality.
Hospital stays	Logistic regression.	Poisson/negative binomial regression of counts (mean rate of hospital stays).
Death	Logistic regression.	Cox PH model for time from randomisation to death.
Secondary - Antimicrobial		

Resistance		
Presence of Gram-negative isolates in stools	Two logistic regression (stool sample finding at 3/12 months separately) controlling for baseline stool sample finding.	
Vancomycin resistant enterococci in stools	Two logistic regressions (stool sample finding at 3/12 months separately) controlling for baseline stool sample finding.	
Secondary - Mechanistic		
Immune parameters -Immune cell phenotypes -TLR ligand stimulated cytokines/chemokines -Plasma cytokines/chemokines -Monocyte and neutrophil phagocytosis -Flu vaccine response	Linear regression.	Transformation for normality.

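### Section 18.2 leaves the log scale for influenza titre and cytokine/chemokine levels to sensitivity analyses, at a cost in power and interpretability

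*Protocol*

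**What the plan says.** The table in Protocol section 18.2 has separate columns for the main analysis and for "Sensitivity analyses".

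- **Influenza titre.** The row "Flu vaccine response - titer" has linear regression as the main analysis and "Transformations for normality" in the sensitivity column. Section 5.1 gives the measurement as "Blood sample - Haemagglutinin inhibition assay and antibody titers".
- **Immune parameters.** One row covers immune cell phenotypes, TLR ligand stimulated cytokines/chemokines, "Plasma cytokines/chemokines", phagocytosis and, again, flu vaccine response. It has the same layout: linear regression as main, "Transformation for normality" as sensitivity.
- **Seroconversion and seroprotection.** These have their own row, analysed by logistic regression.

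Section 18.1 names Poisson, linear, logistic and Cox models for the secondary outcomes and does not mention a log scale. Neither section mentions a geometric mean or a rule for values below a detection limit.

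On numbers, section 15.3 says: "For a sample of around 100 trial participants some additional immunology work". For the influenza work it says only: "A sub-set of patients will be asked to provide a blood sample on the day of". No size is given for that sub-study. The protocol states no SD, effect size or power for titres or cytokines.

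**The concern.** An HI titre is ordinarily the last positive dilution in a doubling series, with values below the first dilution recorded as one constant. Differences on such a scale are ratios. Cytokine and chemokine concentrations are usually right-skewed. Both statements are general knowledge about the assays and are not in the protocol.

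If the main model is fitted to untransformed values, the highest responders dominate both the arm means and the residual variance. The estimate is then a difference in arithmetic means. That does not correspond to the fold-change by which seroconversion is ordinarily defined.

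Enhanced influenza vaccine response and altered cytokine/chemokine response to TLR agonists are two of the three parts of the mechanisms hypothesis in section 5. With about 100 people in the immunology work, a null result caused by lost power could be read as absence of a mechanism.

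**Working it through.** **No figure to reproduce.** The protocol makes no power statement for these outcomes, so the size can only be illustrated. All distributional inputs below are assumptions.

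**Titre inputs**
- The underlying titre is log-normal with control median 1:40 and log2 SD of 1.5, 2.0 or 2.5.
- Readings are 5 below the first dilution, then 10, 20, 40 and so on by doubling. Under the control distribution this puts 9%, 16% and 21% of readings at the floor for the three SDs.
- The geometric mean ratio between arms is 2.
- There are 50 per arm, with 25 and 75 to show the range, because the influenza sub-study size is not stated.
- The test is a two-sided 5% two-sample t-test, equivalent to linear regression on arm without covariates, with 20,000 simulated trials per scenario. The top of the dilution series is capped at 1:2560.

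| Per arm | log2 SD | Power, log2 titre | Power, untransformed |
|---|---|---|---|
| 25 | 1.5 | 62% | 43% |
| 25 | 2.0 | 40% | 21% |
| 25 | 2.5 | 28% | 13% |
| 50 | 1.5 | 90% | 72% |
| 50 | 2.0 | 68% | 40% |
| 50 | 2.5 | 49% | 26% |
| 75 | 1.5 | 98% | 87% |
| 75 | 2.0 | 84% | 55% |
| 75 | 2.5 | 66% | 37% |

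Without a cap on the series, untransformed power at 50 per arm is 71%, 38% and about 20% for the three SDs, and log-scale power hardly moves. This is why the SD 2.5 figure is given as 20-26%.

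**Influence of high values.** Across these scenarios the top 10% of titres in an arm carry 61% to 87% of the sum of squares untransformed, against 28% to 37% on the log2 scale.

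**Cytokine inputs.** Concentrations are log-normal with 50 per arm (half of about 100, before any loss). The ratio is set at exp(0.57 × SD) so that log-scale power is about 80%.

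| ln SD | Ratio | Power, log | Power, untransformed | Loss |
|---|---|---|---|---|
| 0.5 | exp(0.285) = 1.33 | 80% | 75% | 5 points |
| 1.0 | exp(0.570) = 1.77 | 80% | 63% | 17 points |
| 1.3 | exp(0.741) = 2.10 | 80% | 51% | 29 points |

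At a fixed ratio of 1.5 and 50 per arm, log v untransformed power is 71% v 58% (ln SD 0.8), 52% v 36% (1.0) and 27% v 13% (1.5).

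**Type I error.** With no true effect, the untransformed test rejects in 2.5% to 4.2% of titre trials and 3.0% to 4.7% of cytokine trials, against a nominal 5%. It is somewhat conservative and is not inflated.

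**The case against.** **The protocol never says the main model is untransformed.** This is true; it is inferred from the columns. The same sensitivity column holds negative binomial regression, which section 18.1 treats as the model to use when counts are over-dispersed. By analogy, transformation might be a fallback for the main model. But the negative binomial entries state their trigger and section 18.1 repeats it. The transformation entries have no trigger and section 18.1 does not mention them. Even as a fallback, the main scale would be chosen after seeing the data. The same edit settles both readings.

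**Scale and floor handling belong in the SAP.** The exact below-floor rule may well sit there. The order of main and sensitivity analysis, however, is something this table already fixes.

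**The inputs come from outside the protocol.** This stands. The dilution scheme, floor, SDs and ratios are assumed. The figure of about 100 applies to the immunology work, so 50 per arm is an assumption for the titres.

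**Vaccine response is partly covered.** This also stands. Seroconversion and seroprotection are analysed separately and do not depend on the scale chosen for the titre model. That does nothing for the cytokines.

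**Stronger readings.** A reader might infer that a few values always swamp the comparison, or that the plan risks bias or false positives. Neither is supported. At ln SD 0.5 the loss is about 5 points, and type I error is not inflated.

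**Conclusion.** The point holds as one of efficiency and interpretability in secondary mechanistic outcomes. On its natural reading, section 18.2 makes the less suitable scale the main one for influenza titre and for cytokines/chemokines.

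Untransformed power was lower in every simulated scenario with a true effect. The loss ranged from a few points to about half of the available power, depending on a spread and, for titres, a sub-study size that the protocol does not give. The conclusion also rests on the usual properties of HI titres and cytokine concentrations. The primary outcome is not touched. The change should be made because it is nearly free and serves two of the three mechanistic hypotheses.

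**What to change.** In the section 18.2 table:

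1. For influenza titre, make linear regression of log titre (log2 is convenient) the main analysis. State in advance how values below the first dilution are handled, for example set to half of that dilution. Report a ratio of geometric mean titres.
2. For plasma and TLR-stimulated cytokines/chemokines, make linear regression of log concentration the main analysis and report geometric mean ratios.
3. Move the untransformed regression for these outcomes to the sensitivity column.
4. Flu vaccine response also appears in the immune-parameter row, so make that entry agree with the titre row.
5. Leave the logistic analyses of seroconversion and seroprotection as they are.

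The cost is an edit to a few table entries. No new data are needed. The only downside is that effects are reported as ratios instead of differences.
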